8.2.2 Special Assays or Procedures

8.2.2.1 Plaque Sample Collection, Processing and Analysis for Safety Assessments

A plaque sample will be obtained from every subject at the Baseline Visit, Day 14, and Day 28, the conclusion of the experimental period. These plaque samples of oral flora will be analyzed for any increase in opportunistic or pathogenic bacteria. Supragingival plaque will be obtained from 6 sites in the mouth (the mesiobuccal surfaces of the Ramfjord teeth). Samples will be placed in transport media for DNA checkerboard probe analysis (DNA-DNA hybridization assay) and analyzed according to the method of Socransky (Socransky, Smith et al. 1994, Socransky, Haffajee et al. 2004). Samples will be analyzed for the presence of *Fusobacterium nucleatum subspecies vincentii*, *Campylobacter concisus*, *Campylobacter rectus*, *Tannerella forsythensis*, *Prevotella intermedia*, *Prevotella nigrescens*, *Porphyromonas gingivalis*, *Capnocytophaga sputigena*, *Streptococcus oralis*, *Actinomyces naeslundii*, *Actinomyces israeli*, *Eubacterium brachy*, *Eikenella corrodens*, and spirochetes. The technique has been validated by several laboratories and found to be accurate, sensitive (detects 10^4 or more bacteria), and specific when carefully selected DNA probes are used.

8.2.2.2 Gingival Crevicular Fluid Collection and Analysis

Crevicular fluid samples from the mesiobuccal sites of the 4 first molar teeth will be collected using paper strips (Periopaper) furnished by the manufacturers of the Periotron 8000, the instrument used for measurement of crevicular fluid volume. The sample strip will be placed in a pre-labeled vial, snap frozen in liquid nitrogen, and stored at -80°C . Levels of IL-1 β in GCF will be determined by ELISA.

8.2.2.3 Plasma Levels of BLXA4-ME and SPM Profiling in Plasma and Serum

Blood will be collected at Baseline and on Day 28 to measure absorption of BLXA4-ME through the oral mucosa. Labeled plasma specimens will be sent to Avanti Polar Lipids for assay using a liquid chromatography-tandem mass spectrometry technique.

In addition, SPMs (lipoxins and resolvins) will be profiled in serum and plasma samples. Labeled plasma and serum specimens will be sent to laboratory of [name] at Brigham and Women's Hospital, Boston for lipidomics assay using liquid chromatography-tandem mass spectrometry technique.

8.2.3 Specimen Preparation, Handling, and Storage

Specimen preparation for the various assays is described in the Manual of Procedures. Assays on plaque and GCF samples will be performed at the Forsyth Institute laboratories; these samples are stored at -80°C until time of assay. Blood and urine for safety labs will be sent to a commercial clinical laboratory on the day the samples are collected. Frozen plasma specimens for BLXA4 measurement will be sent to the laboratory at Avanti Polar Lipids. Additional frozen plasma and serum specimens for SPM profiling will be sent to [name] laboratory at Brigham and Women's Hospital, Boston.

9 ASSESSMENT OF SAFETY

9.1 Specification of Safety Parameters

Parameters used to assess safety will include AEs spontaneously reported by the subject or observed by the investigator, solicited AEs captured by review of the memory aid while interviewing the subject, clinical laboratory values (reviewed by the on-site medical monitor), oral cavity examination, vital signs, and increases in pathogenic bacterial flora identified in plaque samples. All AEs will be coded by system organ class and preferred term according to the terminology of the Medical Dictionary for Regulatory Activities.

Monitoring of AEs will be conducted throughout the study. New AEs, including SAEs, will be captured through the final study visit. In addition, all AEs will be captured at the final telephone follow-up conducted 2 months after the last use of study product. Adverse events will be followed in accordance with Good Clinical Practice. Serious adverse events will be immediately reported to the IND sponsor, to NIDCR, and to the IRB within 24 hours of becoming aware of the event, and will be monitored until they are resolved or are clearly determined to be due to a subject's stable or chronic condition or intercurrent illness(es). Unanticipated problems (UPs) will also be captured and reported to the IRB and FDA as required by regulation.

9.1.1 Adverse Events

International Conference on Harmonisation (ICH) E6 defines an AE as any untoward medical occurrence in a patient or clinical investigation subject administered a pharmaceutical product regardless of its causal relationship to the study treatment. An AE can therefore be any unfavorable and unintended sign (including an abnormal laboratory finding), symptom, or disease temporally associated with the use of medicinal (investigational) product. The occurrence of an AE may come to the attention of study

personnel during study visits and interviews of a study subject presenting for medical care, or upon review by a study monitor.

All AEs including local and systemic reactions not meeting the criteria for SAEs should be captured. Information to be collected includes event description, time of onset, clinician's assessment of severity, relationship to study product (assessed only by those with the training and authority to make a diagnosis, which would include MD, DO, physician assistant, nurse practitioner, DDS or DMD, dental hygienist), and time of resolution/stabilization of the event. All AEs occurring while on study must be documented appropriately regardless of relationship. All AEs will be followed to adequate resolution or stabilization.

Any medical condition that is present at the time that the subject is screened should be considered as baseline and not reported as an AE. However, if it deteriorates at any time during the study, it should be recorded as an AE.

9.1.2 *Solicited Adverse Events from the Memory Aid*

When the subject returns for follow-up visits, he or she will be instructed to bring the memory aid. Study staff will review the data recorded on the memory aid. The information obtained from the interview will be recorded for the study.

9.1.3 *Serious Adverse Events*

An SAE is an AE that meets 1 or more of the following criteria:

- Results in death
- Is life-threatening (places the subject at immediate risk of death from the event as it occurred)
- Results in inpatient hospitalization or prolongation of existing hospitalization
- Results in a persistent or significant disability or incapacity
- Results in a congenital anomaly or birth defect

An important medical event that may not result in death, be life-threatening, or require hospitalization may be considered an SAE when, based upon appropriate medical judgment, the event may jeopardize the subject and may require medical or surgical intervention to prevent one of the outcomes listed in this definition.

All SAEs will be:

- Reviewed and evaluated by a study clinician;
- Recorded for the study;
- Followed through resolution by a study clinician.

9.1.4 Unanticipated Problems

The Office for Human Research Protections (OHRP) considers UPs involving risks to subjects or others to include, in general, any incident, experience, or outcome that meets all of the following criteria:

- Unexpected in terms of nature, severity, or frequency given (a) the research procedures that are described in the protocol-related documents, such as the IRB-approved research protocol and informed consent document; and (b) the characteristics of the subject population being studied;
- Related or possibly related to participation in the research (“possibly related” means there is a reasonable possibility that the incident, experience, or outcome may have been caused by the procedures involved in the research); and
- Suggests that the research places subjects or others at a greater risk of harm (including physical, psychological, economic, or social harm) than was previously known or recognized.

Because the occurrence of an incident, experience, or outcome that meets the above 3 criteria will generally require changes in the research to protect the safety or welfare of subjects or others, any such occurrence will be promptly reported to the IRB, the medical monitor, and the Data and Safety Monitoring Board (DSMB) Chair.

Unanticipated problems will be captured and reported throughout the study.

9.2 Time Period and Frequency for Event Assessment and Follow-Up

Adverse events will be followed until resolved or considered stable. Phone calls or extra visits may be performed to follow up the AE. The subject will be questioned on the AE and whether it continues or is resolved at the time of the study visit, and whether the subject received any treatment specifically for the AE. The AE data will be updated and a follow-up report will be submitted to the IND Sponsor, NIDCR, and the IRB.

All unresolved AEs will be followed by the investigator until the events are resolved, the subject is lost to follow-up, or the AE is otherwise explained. At the last scheduled visit, the investigator will instruct each subject to report any subsequent event(s) that the

subject, or the subject's personal physician, believes might reasonably be related to participation in this study. The investigator will notify the IND sponsor, NIDCR, and the IRB of any death or AE occurring at any time after a subject has discontinued or terminated study participation, if the death or AE may reasonably be related to this study.

9.3 Characteristics of an Adverse Event

All AEs must be graded for relationship to study product, expectedness, and severity.

9.3.1 Relationship to Study Intervention

The clinician's assessment of an AE's relationship to test article is part of the documentation process, but it is not a factor in determining what is or is not reported in the study. If there is any doubt as to whether a clinical observation is an AE, the event should be reported. All AEs must have their relationship to study product assessed using the following terms:

- Related (possible, probable, definite) events meet 1 or more of the following criteria:
 - The event is known to occur with the study intervention.
 - There is a temporal relationship between the intervention and event onset.
 - The event abates when the intervention is discontinued.
 - The event reappears upon a rechallenge with the intervention.
- Not related (unlikely, not related) events meet 1 of the following criteria:
 - There is no temporal relationship between the intervention and event onset.
 - An alternate etiology has been established.

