2.5 Potential Risks and Benefits

2.5.1 Potential Risks

BLXA4-ME topical oral rinse is intended for administration as an oral rinse (mouthwash) and is not intended for ingestion. For this study, BLXA4-ME will be applied topically as an oral rinse that will be held in the mouth for 45 seconds each day for 28 days. Potential risks include oral irritation from use of the rinse. In a preclinical 28-day oral irritancy study in rats with abraded oral mucosa, transient erythema and edema of the oral mucosa were noted in animals treated with either BLXA4-ME or a saline solution used as a control. Microscopic examination of oral tissues showed no differences between rats treated with BLXA4-ME and control rats treated with saline. In this Phase 1/2 safety study, oral tissues will be closely monitored for signs of inflammation and irritancy, and product administration will be discontinued if toxicity develops. Because the investigational compound may be absorbed through the oral mucosa, blood and urine for safety laboratory tests will be collected from all subjects at screening and 14 and 28 days after initial product administration. Treatment of gingivitis has the potential to conceal the presence of the more serious condition of periodontitis; therefore, subjects will be monitored for development or progression of periodontitis, using clinical periodontal measurements. In addition, oral flora will be analyzed to detect any increase in pathogenic organisms.

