9.5 Rules for Study Suspension or Discontinuation

The NIDCR medical monitor will review all SAEs and UPs in an expedited fashion. In the event of unacceptable toxicity, the trial will be stopped prematurely to prevent harm to subjects. In addition, any injuries, SAEs, or other unexpected AEs involving risk to subjects or others, and occurring at a frequency above that considered acceptable by the investigators, IND sponsor, NIDCR, or IRB, may result in a temporary or permanent halt to the study. The study may be suspended for a safety review and consideration of study discontinuation if:

- One or more subjects experiences a clinically significant event or laboratory abnormality determined to be Grade 3 or higher and related (possibly, probably, definitely) to use of the investigational product;
- Two or more subjects experience a similar event determined to be Grade 2 or higher and related (possibly, probably, definitely) to use of the investigational product;
- One or more subjects experiences a Grade 2 or higher event that does not resolve within 14 days.

The NIDCR medical monitor or DSMB may request to be unblinded to the entire study when evaluating whether to suspend or discontinue the study. In the event of study unblinding, a non-study statistician will be assigned as the “unblinded statistician” to assist in unblinding and any safety review.

Any proposed changes in the consent form or research procedures resulting from any safety findings are to be submitted by the principal investigator to the IRB for approval.

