9. EFFICACY EVALUATION

9.1 Overview of Efficacy Analysis Issues

9.1.1 Handling of Dropouts and Missing Data

Subjects that dropout or are withdrawn prior to Day 14 will be replaced in the Efficacy Population. The mixed models analyses (described in the sections below) will automatically adjust for any missing values provided the missing values are missing at random; and thus, no additional imputation is necessary for missing values that are missing at random.

Missing observations are “not missing at random” if their missing-ness is possibly correlated with disease progression or efficacy. Missing efficacy observations due to missed visits or early study withdrawal will be deemed “not missing at random” if there were any treatment-emergent AE (TEAE) prior to or concurrent with a subject’s missed visit and the relationship between the TEAE and study drug was rated as “Possible”, “Probable”, or “Definite”.

If more than 5% of a given efficacy endpoint is missing, or any missing observations are deemed “missing not at random” then a sensitivity analysis will be performed by repeating the given efficacy analysis with all missing values imputed using “last observation carried forward”. The sensitivity analysis will also be triggered if for any other reason the principle investigator suspects that missing values may bias the analysis. The reasons any sensitivity analyses are triggered will be footnoted in the sensitivity analysis tables.

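### Protocol 9.3.1 lets one adverse event meet both the Related and the Not related definitions, and neither document says which prevails

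*Protocol*

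**What the plan says.** Protocol 9.3.1 gives two lists.

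- Related: "Related (possible, probable, definite) events meet 1 or more of the following criteria". The four criteria are a known effect of the intervention, timing ("There is a temporal relationship between the intervention and event onset"), abatement when the intervention stops, and recurrence on rechallenge.
- Not related: "Not related (unlikely, not related) events meet 1 of the following criteria". The two criteria are no temporal relationship, and "An alternate etiology has been established".

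Temporal relationship is not defined. No sentence makes the categories exclusive or says which prevails. The same section says of the relatedness assessment that "it is not a factor in determining what is or is not reported in the study".

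The code is used in several places:

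- Protocol 12.5.1 and SAP 8.4 tabulate events by relationship.
- Protocol 9.5 requires relatedness in two of its three suspension criteria: the one for Grade 3 or higher, and the one for two or more similar Grade 2 or higher events.
- Protocol 9.4.3 sends serious, unexpected and related events to the FDA within 7 or 15 calendar days. Serious events coded not related go in an annual summary.
- SAP 8.2 and 9.1.1 use it as one trigger for a missing-data sensitivity analysis, where the "relationship between the TEAE and study drug was rated as" possible, probable or definite.

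Protocol 9.3 requires every event to be graded for relationship to study product. SAP 8.4 counts a missing relationship as definite/certain and makes no exception for the no-rinse arm.

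**The concern.** A causality rule should return one answer for one set of facts. This one can return two. The rinse is "held in the mouth for 45 seconds each day for 28 days", so an illness that starts during treatment starts close to a dose. If its cause is then established as something else, one list supports Related and the other supports Not related. Protocol 9.1.1 allows several professions to rate relationship, from physicians to dental hygienists, so the written rule is what keeps raters consistent.

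Three things are at stake. The related-event tables could reflect how raters resolved the overlap rather than the events themselves. The same Grade 2 or Grade 3 events could count toward a suspension review or not. A serious, unexpected event could go to the FDA on the 7- or 15-day clock or in the annual summary.

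The no-rinse arm raises a related problem. These subjects receive no study drug, yet a blank relationship field for one of them would be tabulated as definite/certain.

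**Working it through.** The documents attach no figure to this rule, so there is none to reproduce. The check is logical, followed by an illustration.

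**Step 1. Inputs (Protocol 9.3.1).** Five yes/no facts: K = known effect, T = temporal relationship, A = abates on stopping, R = recurs on rechallenge, E = alternate etiology established.

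- Related = K or T or A or R
- Not related = (not T) or E

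**Step 2. All 2^5 = 32 combinations.**

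| Facts | Patterns | Result |
|---|---|---|
| T yes, E no | 8 | Related only |
| T yes, E yes | 8 | Both |
| T no, at least one of K, A, R | 7 × 2 = 14 | Both |
| T no, none of K, A, R | 1 × 2 = 2 | Not related only |

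Both: 8 + 14 = 22. Total: 8 + 22 + 2 = 32. No pattern is left unclassified. The 22 is a count of logical patterns, not a share of events, and some of the 14 patterns without timing would be unusual in practice. The eight with timing and an established alternate cause are the practical ones. They stay in both lists even if the Not related rule is read as exactly one criterion rather than at least one.

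**Step 3. Search for a tie-break.** Protocol 9.1.1 says who may rate relationship. Protocol 9.3.2 says who assesses possibly related events and when an event is unexpected. SAP 8.4 covers a missing relationship, and repeated events with different ratings. None says what to do when both lists are met.

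**Step 4. Illustration only.** Assume a share p of subjects has a similar illness of Grade 2 or higher, with an established other cause, during treatment. Neither document gives p. For n subjects,

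P(at least 2) = 1 − (1 − p)^n − n·p·(1 − p)^(n−1).

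For n = 50 (the active arm) and p = 2%: 1 − 0.364 − 0.372 = 0.264.

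| p | n = 50 (active arm) | n = 100 (both rinse arms, rated blind) |
|---|---|---|
| 1% | 8.9% | – |
| 2% | 26.4% | 59.7% |
| 5% | 72.1% | 96.3% |
| 10% | 96.6% | – |

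If every such case is coded by timing, these are the chances that the two-subject criterion in Protocol 9.5 is met. If every case is coded by etiology, these illnesses contribute nothing to it. The gap between the two readings is the point. The percentages depend entirely on the assumed p.

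**The case against.** The strongest reply is that relatedness is a clinical judgment. Protocol 9.3.1 calls it the clinician's assessment, 9.1.1 restricts it to those trained and authorised to diagnose, and 9.3.2 adds the IND sponsor, the investigator and the NIDCR medical monitor. A clinician may take a temporal relationship to mean more than onset during treatment. This stands, and it defeats one tempting inference: that every event in a rinse subject up to Day 28 must be coded Related. The documents do not define the term that way. Overlap through timing also needs an alternate cause that is actually established. Without one, timing alone gives Related only. But judgment about the facts does not settle which list wins once both are met.

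A reader might also infer that ordinary illness would halt the trial. The text does not support this. Protocol 9.5 says the study may be suspended for review, the event must reach Grade 2 and be similar across subjects, and the incidence above is assumed. The third criterion, a Grade 2 or higher event not resolved within 14 days, does not use relatedness.

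Nor does the overlap undermine the primary safety evaluation as a whole. Protocol 3.2.1 defines the primary outcome by the incidence of adverse events, periodontitis and oral flora. All treatment-emergent events are summarised by arm whatever their code, and recording does not depend on relatedness.

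The missing-data trigger is a minor consequence. The same sensitivity analysis runs if more than 5% of values are missing or if the investigator suspects bias, and the plan assumes 20% attrition. Once triggered, it imputes all missing values whatever their relatedness. Replacing subjects who leave before Day 14 lowers missingness in the Efficacy Population, but relatedness would matter only if missingness stayed at or below 5%.

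Finally, coding a no-rinse event as not related to a product never received is reasonable. The fault there is confined to the default for missing values.

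**Conclusion.** The concern holds as a contradiction in a stated rule. In 22 of 32 fact patterns, including all eight that combine timing with an established alternate cause, Protocol 9.3.1 supports both codes and nothing decides between them. The effect falls on the related-event summaries, two of three discretionary suspension criteria and expedited FDA reporting. Event recording and the comparison of all treatment-emergent events by arm are not affected.

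The logical result takes the lists as written and needs no assumption about incidence. How many real events would be coded inconsistently cannot be derived from the documents, because it depends on background illness, on how often a cause is established and on how raters read the timing criterion.

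**What to change.** - **Protocol 9.3.1:** reconcile the two lists so that each event falls in exactly one category, either by mutually exclusive definitions or by a stated order of precedence. The choice of causality rule is the sponsor's, since it feeds Protocol 9.4.3 and 9.5.
- **SAP 8.4:** state that counting a missing relationship as definite/certain does not apply to no-rinse subjects, and present relatedness to study drug for the two rinse arms.

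The cost is a few sentences and no new data. Related counts may change, in a direction that depends on the rule chosen.

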9.3.2 Expectedness

This trial involves the first use of the BLXA4-ME oral rinse in humans; therefore, no human data exist to classify expectedness of events. In a preclinical 28-day oral irritancy study in rats, transient erythema and edema of the oral mucosa were noted in animals treated with either BLXA4-ME or a saline solution used as a control. For this study, the IND sponsor, the study investigator, and the NIDCR medical monitor will be responsible for assessing AEs that may be related to product use. An AE will be considered unexpected if the nature, severity, or frequency of the event is not consistent with the risk information described in the protocol or the Investigator's Brochure or discussed with the subject during the informed consent process.

